5.5 Identification of Non-Responders

As E-CLAD UK is an intervention study with an efficacy endpoint, it is very important that every possible effort is made to allow participants to safely complete the study as *per protocol*. The aim of this study is to determine if ECP is efficacious in stabilising CLAD and therefore it is critical that sufficient ECP treatment is given to participants in the treatment arm to perform this assessment. All participants will be assessed at 12 weeks to assess response and identify non-responders in both groups.

If there is a >20% fall in FEV1 or FVC from baseline either within or at the 12-week assessment, then it is important for site PIs to confirm if this is due to progressive CLAD and not an intercurrent infection, new or progressive large airway obstruction or an extra-pulmonary cause. Participants can only be identified as a non-responder when a >20% fall in FEV1 or FVC is confirmed as being due to progressive CLAD. If there is any doubt that the >20% fall in FEV1 or FVC is due to progressive CLAD, then the participant should remain in the study and possible other causes should be fully treated and lung function reassessed at a suitable interval not exceeding the next study visit.

For any participants where CLAD progression means further rescue treatment is required which is not standard of care for patients suffering from CLAD (for example TLI), it is important to note that these participants must be withdrawn from the E-CLAD UK trial prior to any rescue treatment being given.

A decision Tree is provided in Appendix 6 regarding identifying non-responders and whether they are able to continue in the trial depending on their circumstances.

5.5.1 Participants in the ECP + SOC arm

At 12 weeks participants will be reviewed to assess response to treatment. Participants will have received 6 of the total 9 cycles of ECP planned in the treatment arm. Six cycles of ECP provides a meaningful treatment exposure and furthermore allows time for identification of participants who have rapidly progressive CLAD disease despite receiving an intensive short course of ECP therapy.

If at 12 weeks, either FEV1 or FVC has >20% decline from baseline measurements at trial entry due to progressive CLAD, they will be deemed non-responders to ECP plus SOC due to an insufficient therapeutic effect.

If a participant in the ECP plus SOC arm has a >20% fall in FEV1 or FVC from study baseline before their 12 week study visit and this is confirmed to be due to very rapidly progressive CLAD, then the site PI should assess the balance of risks in continuing with ECP treatment until 6 cycles have been completed or declaring the patient a non-responder before a meaningful exposure to ECP therapy has been achieved.

None of the potential rescue therapies that could be offered to participants discontinuing ECP therapy in the study have proven efficacy in treatment of CLAD in clinical trials and so this should be factored in any decision making by the site PI in identifying a participant as a non-responder before their 12 weeks study visit. A potential approach in those with a >20% fall in FEV1 or FVC before 12 weeks is to

prepare for access to a rescue treatment while also continuing to deliver ECP in the study so that this can commence promptly after the 12 weeks study visit.

In such situations, it is recommended that the site PI discusses the circumstances with the study CI to help ensure consistency of approach across centres in such cases.

Participants in the Newcastle mechanistic sub-study cohort who are classified as a non-responder at the 12 week assessment should still have their pre-ECP research blood sample collected even if they do not go on and have a 7th cycle of ECP treatment. This is to allow comparison with the baseline sample.

5.5.2 Participants in the SOC arm

If at 12 weeks, either FEV1 or FVC has >20% decline from baseline measurements at trial entry due to progressive CLAD, they will be deemed non-responders to SOC.

If a participant in the SOC arm has a >20% fall in FEV1 or FVC from study baseline before their 12 week study visit and this is confirmed to be due to very rapidly progressive CLAD, then the site PI should assess the balance of risks in continuing with SOC or consider introducing a rescue treatment outside the trial.

In such situations, it is recommended that the site PI discusses the circumstances with the study CI to help ensure consistency of approach across centres in such cases.

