2. OBJECTIVES AND OUTCOME MEASURES

2.1 Primary Objective

To determine if ECP therapy plus SOC is more effective at stabilising lung function in lung transplant recipients with CLAD compared to SOC alone.

Lung function stabilisation will be derived from change in FEV1 and FVC at 12 and 24 weeks compared to baseline at study entry. The primary outcome measure is a composite responder outcome, which is defined as both 'lung function stabilisation' from baseline to 24 weeks and 'no rapid decline' as measured from baseline to 12 weeks (see section 7 for definitions).

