7.3 Lung Function

Lung function stabilisation – defined as a less than or equal to a 10% loss in FEV1 and FVC from study baseline to 24 weeks.

Rapid decline – defined as a greater than 20% fall in FEV1 or FVC in the first 12 weeks from study baseline.

Non-responders – As outlined in the study flow chart in Section 3.3, a non-responder is defined as someone who experiences a decline in FEV1 or FVC of more than 10% at 24 weeks compared to baseline readings due to progressive CLAD. A non-responder may also be someone with a decline in FEV1 or FVC of >20% within 12 weeks of the baseline visit that is confirmed as being due to progressive CLAD.

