10.1 Sample Size Calculation

Our proposed sample size is 90 patients. We used published evidence to underpin our sample size calculations. Todd et al reported changes in longitudinal lung function in 213 CLAD patients who did not receive ECP; 27% had a <10% loss in FEV1 within 6 months, equating to stabilisation. We assume conservatively that in the SOC arm, 30% patients will be responders. The three largest ECP in CLAD studies show 54-61% patients had <10% decline in FEV1 within 6 months; we therefore assume a 55% stabilisation rate in the ECP arm. With 90 patients randomised 1:1 between SOC and ECP arms, we would have 80% power (5% one-sided type I error rate) to detect a difference when the ECP arm has a 55% response rate and the SOC arm a 30% response rate. This calculation assumes Barnard's exact test is used in the analysis.

As the primary endpoint is a composite responder endpoint, our primary analysis will utilise the augmented binary method to test the difference in response rate as the primary analysis (see Section 10.10.2). Previous work has shown that the augmented binary method increases the power of the analysis equivalent to increasing the sample size by at least 35% without any inflation in the type 1 error-rate. Even allowing for 10% of patients dropping out, we are thus confident power will be above 85% for this analysis, and believe it is likely to be above 90%. Conservatively, for the augmented binary analysis we believe the maximum number of patients required to achieve 80% power is 68.

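### The protocol does not settle whether a fall of more than 20% before week 12 counts against a patient, and its advice after such a fall differs by arm

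*Protocol*

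**What the plan says.** **Timing.** Section 7.3 describes rapid decline as "defined as a greater than 20% fall in FEV1 or FVC in the first 12 weeks from study baseline", with no mention of cause. Its separate definition of a non-responder adds that a confirmed fall of that size within 12 weeks may also make someone a non-responder. Section 5.5 tells sites to act on such a fall whether it appears before or at the 12-week assessment, and allows non-responder status only once progressive CLAD is confirmed. Section 10.3.1 builds the responder outcome from the absence of rapid decline at week 12 and a loss of at most 10% at week 24. Its second sensitivity analysis also refers only to falls at week 12. Section 2.1 has "as measured from baseline to 12 weeks" and section 3.1 is worded similarly.

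**Action after an early fall.** Sections 5.5.1 and 5.5.2 share a trigger: a fall above 20% before the 12-week visit, confirmed as very rapidly progressive CLAD.
- SOC (5.5.2): "then the site PI should assess the balance of risks in continuing with SOC or consider introducing a rescue treatment outside the trial".
- ECP (5.5.1): the PI weighs completing six cycles against declaring non-response before meaningful exposure, is reminded that no rescue therapy has proven efficacy, and is offered the approach to "prepare for access to a rescue treatment while also continuing to deliver ECP in the study" until the 12-week visit.

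**Consequence.** Section 5.5.3 counts non-responders as non-stabilised and requires full withdrawal once rescue starts.

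**The concern.** Two analysts following different sections could classify the same patient differently on the primary endpoint. The patient in question falls more than 20% at week 4 or 8, with CLAD confirmed, and is later back within 20% at week 12 and within 10% at week 24.

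The timing question interacts with the exit advice. If any fall in the first 12 weeks counts, such a patient fails in either arm whatever happens next. If only the week-12 reading counts, a patient who stays can still become a responder, while one who leaves for rescue is fixed as non-stabilised. The ECP text leans towards staying and the SOC text does not. The decision is discretionary and the trial is open-label, so any resulting difference would tend to favour ECP.

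**Working it through.** **1. The passages side by side**

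| Section | When a >20% fall counts | CLAD cause required? |
|---|---|---|
| 7.3, rapid decline | any time in the first 12 weeks | not mentioned |
| 7.3, non-responder | within 12 weeks (may) | yes |
| 5.5 | before or at the 12-week assessment | yes |
| 2.1 | baseline to 12 weeks (either reading) | refers to section 7 |
| 3.1 | baseline to 12 weeks (either reading) | yes |
| 10.3.1 and second sensitivity analysis | at week 12 | not mentioned |

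The clear conflict is 7.3 and 5.5 against 10.3.1. Whether CLAD confirmation is part of the rule also varies.

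**2. The plan's own power figure**

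Section 10.1 claims 80% power at one-sided 5% with 90 patients (45 per arm), "when the ECP arm has a 55% response rate and the SOC arm a 30% response rate". By normal approximation:
- Unpooled SE = √[(0.30×0.70 + 0.55×0.45)/45] = 0.1008. Power = Φ(0.25/0.1008 − 1.645) = 79.8%.
- Pooled null SE = √[2×0.425×0.575/45] = 0.1042. Power = Φ[(0.25 − 1.645×0.1042)/0.1008] = 78.2%.

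An unconditional exact test of the kind named ("This calculation assumes Barnard's exact test is used in the analysis"), with maximum size held at 5%, gives 76.9%. The figure is approximately reproduced, and this point does not depend on it.

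**3. How many patients could be affected**

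The documents give no visit-level variability, so these are assumptions. Percentage change in FEV1 at week t = (μ + σz)·t/24 + e_t − e_0, with z standard normal, σ = 15 or 20 points, and error e of SD 3 to 10 points at every reading including baseline. μ is set so that 30% respond (change ≥ −20 at week 12 and ≥ −10 at week 24). An early crosser is below −20 at week 4 or 8. There were 200,000 simulated patients per row, FEV1 only, with no CLAD-confirmation step.

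| Error SD | σ | Early crosser | …and within 20% at week 12 | …and full responder |
|---|---|---|---|---|
| 3 | 15 | 1.7% | 0.2% | 0.00% |
| 3 | 20 | 4.9% | 0.2% | 0.00% |
| 5 | 15 | 6.3% | 2.1% | 0.06% |
| 5 | 20 | 9.8% | 2.1% | 0.04% |
| 7 | 15 | 13.8% | 5.8% | 0.49% |
| 7 | 20 | 16.8% | 5.4% | 0.46% |
| 10 | 15 | 25.0% | 11.1% | 1.77% |
| 10 | 20 | 27.1% | 10.5% | 1.75% |

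Only the last column changes endpoint status between the two rules. At its highest it is 0.0177 × 45 ≈ 0.8 patients per arm.

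A second set of assumptions took the lower of FEV1 and FVC, a mean 24-week change of −17% (SD 14) and visit noise of SD 5 to 7. It gives 0 to 0.3% without temporary dips. If 5% of visits carry a temporary 20-point dip the share is 1.7 to 1.9%; if 10% do, it is 3.1 to 3.2%.

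**4. What a one-sided loss would do under no true effect**

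Let a share s of SOC patients be would-be responders who left and are scored as failures, with no such loss in ECP. The rejection probability of the exact test is then the sum, over its rejection region, of Bin(45, 0.30 − s) × Bin(45, 0.30):
- s = 0: 4.5%
- s = 1 point: 5.5%
- s = 2 points: 6.7%

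This uses the exact test from the sample-size section, not the augmented binary method planned for the primary analysis.

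**The case against.** A reader might infer that SOC patients can fail at weeks 4, 8 and 12 while ECP patients can fail only at week 12, and that this hands ECP 2 to 3 points. The documents do not support that:
- A SOC patient may stay and is then judged like an ECP patient.
- An ECP patient may be declared a non-responder early, and section 1.3 lets participants in both groups leave before week 12.
- Continuing ECP is offered as one possible approach, not a rule.
- Both sections recommend discussion with the chief investigator for consistency.
- Gains of 2 to 3 points need temporary dips at 5 to 10% of visits and every SOC early crosser leaving. Section 5.5 is designed to screen out such dips: any doubt about CLAD keeps the patient in the study, with other causes treated and lung function reassessed by the next visit.

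A CLAD-confirmed fall that then recovers should also be uncommon, since section 1.1 says no treatment is proven to reverse the damage. If ECP does produce recoveries, that is treatment effect, not bias. Sections 2.1 and 3.1 can be read as meaning the whole interval. The flow chart and decision tree given to sites are not visible in the text reviewed and may be clearer. Follow-up after withdrawal is partly protected by a final assessment at withdrawal and a request to use routine data.

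All of this stands, and it limits the size. It does not remove the conflict between 7.3 and 10.3.1 or the difference in advice between 5.5.1 and 5.5.2.

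**Conclusion.** The protocol contains two timing rules for one component of its primary endpoint, and they can classify the same patient differently. This is a contradiction in the protocol text, not a detail left to the SAP.

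The unequal advice means the ambiguity can favour ECP if the week-12 rule is used. The effect is probably small: near zero without temporary dips at modest noise (SD 3 to 7), and up to about 1.8 points only with reading error of SD 10, before CLAD confirmation. Even that requires every affected SOC patient to leave and every affected ECP patient to stay; if half the SOC patients left, it would be about 0.9 points. Against a 25-point target this would not make the result, but 1 to 2 points would move a nominal one-sided 5% test from 4.5% to between 5.5% and 6.7% under no effect. These sizes rest on assumed linear decline and assumed noise.

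**What to change.** 1. State one timing rule in 2.1, 3.1, 5.5, 7.3 and 10.3.1, and say whether CLAD confirmation is part of it. A confirmed fall above 20% before week 12 should have the same endpoint status in both arms, whatever treatment follows.
2. If the week-12 rule is chosen, the joint model of weeks 12 and 24 can stay as planned. Counting any earlier fall in the primary endpoint would need the model to be extended, because it does not include weeks 4 and 8.
3. Add a stated sensitivity analysis that counts a fall above 20% at any in-clinic visit up to week 12 as non-response in both arms.
4. Reconcile 5.5.1 and 5.5.2. The clinical condition for staying or leaving is for the investigators to set.

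The cost is protocol wording and one derived variable from spirometry already collected. In the sensitivity analysis response rates will be slightly lower, some temporary falls will count as failures, and there will be gaps where home spirometry replaced a clinic reading at week 4 or 8.

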5.5.3 Primary endpoint and treatments for non-responders

Non-responders will be censored and included as 'non-stabilised' in the primary endpoint analysis. Non-responders will be eligible for rescue treatment outside the study. If rescue treatment will be given the participant must be withdrawn fully from the trial at the point that the rescue treatment commences. Use of any rescue treatment is at the discretion of the usual treating lung transplant physician.

5.6 Final Assessment for all participants

Routine clinical data should be assessed prior to commencing research specific assessments at the final assessment schedule for week 24. If the participant has seen a drop in lung function that is believed to be non-CLAD related and reversible, then the final assessment should be rearranged to allow any treatment to take place. The rearranged visit can be up to, but no later than, 30 days after the 24 week date. Unless cancelled for non-CLAD reasons as outlined above, the week 24 visit should take place at 24 weeks +/- 7 days.

The following research specific assessments will be repeated at the final assessment at 24 weeks:

- Full Pulmonary Function Tests (PFT):
 - Spirometry comprising FEV1 and FVC.
 - Flow Volume Loop including FEF25-75
 - Static Lung volumes comprising Total Lung Capacity (TLC) and Residual Volume (RV).
 - Total diffusing capacity (DLCO), alveolar volume (Va) and volume corrected diffusing capacity (KCO).
 - Pulse oximetry at rest.
- 6 MWT
- EQ-5D-5L questionnaire
- SF-36 v2 questionnaire

Where a participant is withdrawn from the study before the final assessment, the final assessment should be carried out as close to the time of withdrawal with the participant's permission.

See withdrawal section 5.12 for further details.

5.7 Additional information and data collection at ECP visits

Participants allocated to receive ECP will attend their respective ECP unit for treatment at 0, 2, 4, 6, 8, 10, 12, 16, 20 weeks. At weeks 4, 8, 12, 16, 20 and 24, data regarding the patient's condition, lung function and changes to CLAD treatment will also be collected and recorded in the eCRF. Where the ECP treatment visit aligns with the follow up assessments (4, 8, 12, and 20 weeks), the research assessments should take place prior to the ECP treatment commencing.

Ideally sites should try to adhere to 14 days between ECP treatment cycles wherever possible. For cycles 1-7 and 28 days for cycles 8 and 9. Where this is not possible there should be a minimum of 10 days between ECP treatment cycles. and a maximum of 21 days between ECP treatment cycles.

The clinical assessments and blood samples taken at the ECP treatment visits are for clinical purposes to ensure it is safe to proceed with treatment and should take place prior to commencing the ECP treatment cycle as per usual clinical practice, matching those normally performed at each ECP unit. Any results necessitating alterations to the standard ECP protocol or deferment of treatment are to be recorded in the eCRF. There are no additional research assessments to be undertaken at each ECP treatment visit.

AE and SAE reporting and concomitant medication review should coincide with each trial visit. For weeks 2, 6 and 10 where patients receive ECP treatment but are not required for routine clinical assessment, details may be collected by the research team via a telephone call to the patient. For information on reporting AEs and SAEs, including those identified during the ECP procedure see section 8.2.

All participants in the ECP arm must be followed up for a minimum of 4 weeks after the last ECP treatment and any adverse events noted during this time reported as per section 9.

A data card comes as standard with each ECP treatment kit. This is inserted into the machine and collects data about the machine settings and the way the treatment went. For participants in the E-CLAD UK trial we are asking ECP teams to follow the steps below:

1. Record the ID of the ECP treatment kit on the participants treatment record – this links the participant to the kit that was used to treat them and the card that will contain the treatment data.
2. The ECP specialist nurse delivering the treatment for an ECLAD-UK participant to enter 9999 into the operator ID box. This will allow the Therakos team to recognise the entry as an E-CLAD UK participant treatment.

This will allow the data from the data card to link back to the participant and will provide an additional safety net in case there were any adverse events associated with a treatment.

There is a UVA guidance document that should be handed out to participants randomised to the ECP arm. This provides participants with a reminder regarding sunglasses and sun cream requirements after ECP treatment. There is a trial safety card that must also be handed out to participants randomised to receive ECP to keep with them at all times during trial participation.

Therakos have also provided the trial with a supply of ECP starter packs that include key items such as sunglasses and sunscreen. These should be given to participants randomised to receive ECP. Each site

will be provided with a supply by NCTU. If possible it would therefore be beneficial for the research team to perform randomisation while the participant is still in attendance at the baseline visit, so that the starter pack and UVA guidance document can be provided straight away if required. If this is not possible then the packs/guidance document should be given to the participant at their next appointment and before they commence ECP.

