2.2 Secondary Objectives

To determine how the treatment strategies of ECP therapy plus SOC and SOC alone affect the following outcomes over a 24-week period:

- Change in rate of decline in lung allograft function between before randomisation (available from clinical records) and up to 24 weeks after randomisation, measured by change in FEV1 and FVC (litres/month).
- Absolute change in lung allograft dysfunction from baseline to 24 weeks, measured by FEV1 and FVC (litres).
- Change in exercise capacity from baseline to 24 weeks measured by distance walked (metres) during a 6-minute walk test.
- Change in disease severity from baseline to 24 weeks measured by ISHLT CLAD Stage (1-4).
- Change in health-related quality of life from baseline to 24 weeks measured by SF-36 v2 and EQ-5D-5L.
- Survival at 24 weeks after randomisation (end of study).
- Adverse events (AEs) and Serious adverse events (SAEs) from randomisation to 24 weeks.

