5.4 Follow up assessments and Data Collection

5.4.1 Schedule of Events

Activity	Screening at clinical assessments	Week 0**		Week 2 +/- 7 days	Week 4 +/- 7 days	Week 6 +/- 7 days	Week 8 +/- 7 days	Week 10 +/- 7 days	Week 12 +/- 7 days	Week 16 +/- 7 days	Week 20 +/- 7 days	Week 24 +/- 7 days ****
		Baseline Visit	ECP only* (0-14 days)	ECP only	Research Assessment	ECP only	Research Assessment	ECP only	Research Assessment	Research Assessment	Research Assessment	Research Assessment
Screening												
Screen medical notes	x											
Provide PIS	x											
Initial Eligibility check	x											
Consent												
Informed Consent		x										
Confirmation of eligibility		x										
Pregnancy Test		x										
Randomisation		x										
Safety Bloods (FBC, U&E, LFT)		x										
Routine Data Collection												
Demographics		x										
PMH		x										
Clinical/physical assessment		x			x		X		x	x	x	x
Routine blood tests***					x		X		x	x	x	x
Chest X-ray findings		x			x		X		x	x	x	x
Medication review		x			x		X		x	x	x	x
PFT Spirometry (FEV/FVC)		x			x		x		x	x	x	x
Survival status												x
Research assessments												
Research Bloods		x							x			x
6 MWT		x										x
EQ-5D-5L		x										x
SF-36 v2		x										x
ISHLT CLAD score		x										x
Research full PFT		x										x
AE & SAE Reporting			x	x	x	x	x	x	x	x	x	x
Assessment of Response									X*****			
Assess if cannula possible or catheter required		x										
ECP arm only												
ECP Cycle (2 days) + clinical bloods			1	2	3	4	5	6	7	8	9	
∞Pre and post ECP (NCL only) (2 x 20mls)			x						x		x	
*The first ECP cycle should ideally take place within 14 days of randomisation. If ECP cycle 1 is >28 days after randomisation this should be documented as a deviation If ECP cycle 1 is >14 days after randomisation then baseline Spirometry should be repeated ****Visit window extended to +30 days if participant believed to have treatable non-CLAD condition at time of planned visit					**Follow up assessments are from date of randomisation in control arm, and from date of commencing ECP for intervention arm. *** Routine Blood Tests – Full Blood Count, Urea and Electrolytes and Liver Function tests ***** For those in the ECP arm participants must have received 6 treatment cycles prior to the formal 12 week assessment of response taking place – see sections 5.4.5 and 5.5.1 for details ∞ Pre and Post ECP research Blood for apoptosis assay in Newcastle participants only for mechanistic sub study							

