5.4.2 Follow up Assessment time points for all participants

Follow up assessments will take place at 4, 8, 12, 16, 20 and 24 weeks (see Schedule of Events in section 5.4.1). For participants in the SOC arm week 0 will be baseline assessment. For participants in the ECP arm week 0 will be from the day the first ECP treatment is commenced. At the 12-week assessment all participants will be reviewed to identify non-responders in both groups (see section 5.5).

Follow up visits should align with routine clinical appointments where possible. Visit windows have been incorporated into the schedule of events (see section 5.4.1) to enable assessments and collection of routine data in line with the regular clinical visits already attended.

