9.2 Recording and Reporting AEs and SAEs

Adverse Events:

All AEs occurring from the time of consent to end of trial participation, must be recorded in the AE eCRF page as well as the participant's medical notes.

Events which are due to the symptomatic deterioration of the participant, and which are expected for participants who have CLAD progression, do not need to be reported as AEs. These events will be recorded in the participant record and will be reported in the eCRF, but not as AEs.

All adverse events which are not associated with the deterioration of the participant or their non-response to treatment will be recorded as AEs, both for participants in the ECP treatment group and also for those in the SOC group. These events include the following:

- Transient fever
- Transient hypotension
- Dizziness / Pre-Syncope
- Nausea
- Vomiting
- Loss of appetite
- Headache
- Fatigue
- Minor photosensitivity reactions
- Local site infections associated with peripheral or central venous catheterisation
- Other Infections of all types: Bacterial Fungal Viral
- Worsening of any baseline medical condition eg hypertension, diabetes, gastro-oesophageal reflux
- Need for blood transfusion
- Need for platelet transfusion

This list is not exhaustive and any other AE which, in the opinion of the investigator is not due to the progression of CLAD, should be reported as an AE.

Serious Adverse Events and Serious Adverse Reactions:

All SAEs occurring from point of consent to end of trial participation (end of the last trial related assessment) must be reported to NCTU on an SAE form and recorded in the AE eCRF page and recorded as serious.

All SARs occurring from the time of first ECP treatment up until the last trial related assessment for the participant at week 24 must be reported to NCTU on an SAE form and also recorded in the AE eCRF page and recorded as serious. All participants in the ECP arm must be followed up for a minimum of 4 weeks after the last ECP treatment.

Following this defined active monitoring period for SARs, investigators are still required to report any SARs or SUSARs they become aware of for all trial participants for the duration of the study (i.e. up until LPLV).

An unscheduled hospitalisation, with any of the following causes, will need to be reported as an SAE:

- Systemic infection associated with central venous catheter use
- Systemic infections associated with peripheral cannulation
- Sepsis of any cause
- Pulmonary embolus

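### Adverse events are compared between arms, but to week 12 ECP participants are asked every 2 weeks and SOC participants every 4, so non-serious events can be expected to look somewhat more frequent under ECP

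*Protocol*

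**What the plan says.** Section 2.2 introduces the secondary outcomes with "To determine how the treatment strategies of ECP therapy plus SOC and SOC alone affect the following outcomes over a 24-week period", and the list includes "Adverse events (AEs) and Serious adverse events (SAEs) from randomisation to 24 weeks". Adverse events are thus an outcome compared between arms. Section 9.2 agrees: events not attributed to deterioration or non-response "will be recorded as AEs, both for participants in the ECP treatment group and also for those in the SOC group".

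The contact pattern is set in three places.

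- **Section 5.4.1, Schedule of Events.** The row "AE & SAE Reporting" has 10 marks: the week 0 ECP visit and weeks 2, 4, 6, 8, 10, 12, 16, 20 and 24. The week 0 ECP visit and weeks 2, 6 and 10 are headed as ECP only.
- **Section 5.4.2, for all participants.** "Follow up assessments will take place at 4, 8, 12, 16, 20 and 24 weeks". Section 3.1 gives the same list.
- **Section 5.7, for the ECP arm.** "Participants allocated to receive ECP will attend their respective ECP unit for treatment at 0, 2, 4, 6, 8, 10, 12, 16, 20 weeks". It adds that "AE and SAE reporting and concomitant medication review should coincide with each trial visit", and allows the research team to collect the details by telephone "For weeks 2, 6 and 10 where patients receive ECP treatment but are not required for routine clinical assessment".

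No contact is scheduled for SOC participants at weeks 2, 6 or 10. Section 5.3.3 states that the trial is unblinded. A footnote to the Schedule of Events starts the follow-up clock at randomisation in the control arm and at the first ECP treatment in the intervention arm.

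**The concern.** Many of the events that section 9.2 lists are brief and known only if the participant mentions them: passing fever, dizziness, nausea, loss of appetite, headache, fatigue. How many are recorded depends on how soon after the event someone asks. Up to week 12 one arm is asked twice as often as the other, so the AE comparison mixes the effect of ECP with the effect of being asked.

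The direction follows from the schedule: any forgetting between contacts raises the captured rate under ECP. The benefit-risk reading of the trial is at stake, mainly for non-specific complaints that could occur in either arm. The arm-specific start of the clock adds a second effect in the same direction on raw counts, because ECP participants can be observed for longer after randomisation.

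**Working it through.** **1. Count of contacts (section 5.4.1, checked against 3.1, 5.4.2 and 5.7)**

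- ECP: weeks 0, 2, 4, 6, 8, 10, 12, 16, 20, 24 = 10.
- SOC: 10 − 4 ECP-only columns = 6 (weeks 4, 8, 12, 16, 20, 24).
- To week 12 the count is 7 against 3. The week 0 ECP session shortens no later recall interval, so the intervals that matter are six of 2 weeks (ECP) against three of 4 weeks (SOC). From week 12 to 24 both arms have three of 4 weeks.

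**2. Size under assumed recall loss**

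The protocol gives no recall rate, so this is an assumption shown over a range. Take equal true rates, and let an event that occurred t weeks before the next contact be reported with probability exp(−λt), where λ = ln 2 / half-life. An interval of d weeks captures (1 − exp(−λd))/λ weeks' worth of events.

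With a half-life of 2 weeks, λ = 0.347. A 2-week interval captures 0.50/0.347 = 1.44 and a 4-week interval 0.75/0.347 = 2.16.

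- ECP: (6 × 1.44 + 3 × 2.16)/24 = 0.63.
- SOC: (6 × 2.16)/24 = 0.54.
- Ratio over 24 weeks: 1.17.
- Ratio in weeks 0 to 12: (6 × 1.44)/(3 × 2.16) = 1.33.

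| Recall half-life (weeks) | Captured, ECP | Captured, SOC | Ratio, 24 weeks | Ratio, weeks 0–12 |
|---|---|---|---|---|
| 2 | 0.63 | 0.54 | 1.17 | 1.33 |
| 4 | 0.78 | 0.72 | 1.09 | 1.17 |
| 8 | 0.88 | 0.85 | 1.04 | 1.09 |
| 16 | 0.94 | 0.92 | 1.02 | 1.04 |
| no loss | 1.00 | 1.00 | 1.00 | 1.00 |

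A simpler assumption gives similar sizes. With 80% reported over a 2-week interval and 60% over 4 weeks, the ratio is 0.80/0.60 = 1.33 to week 12 and (0.80 + 0.60)/(0.60 + 0.60) = 1.17 over 24 weeks. With 90% and 80% it is 1.13 and (0.90 + 0.80)/(0.80 + 0.80) = 1.06.

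**3. Start of the clock**

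If the first ECP comes 2 or 4 weeks after randomisation, the ECP arm is observed for 26 or 28 weeks against 24. With no recall loss, raw counts differ by 26/24 = 1.08 or 28/24 = 1.17. Dividing by follow-up time returns both to 1.00. At a half-life of 2 weeks, the ratio of rates per week from randomisation is 1.18 with a 2-week lag and 1.14 with a 4-week lag, so the recall effect remains after this correction.

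**4. After matching SOC calls at weeks 2, 6 and 10**

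Both arms then have six 2-week and three 4-week intervals, and the ratio is 1.00 at every half-life when there is no lag. At a half-life of 2 weeks, a 2-week lag gives (15.15 + 1.44)/26 = 0.638 against 15.15/24 = 0.631, a ratio of 1.01. A 4-week lag gives (15.15 + 2.16)/28 = 0.618, a ratio of 0.98.

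**5. Restricting the comparison to common visits**

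Events first reported at weeks 2, 6 and 10 would drop out of the ECP arm, while SOC events from the same weeks would still be picked up at weeks 4, 8 and 12. With the 80%/60% figures and equal true rates, ECP contributes 0.5 × 0.80 = 0.40 against 0.60 to week 12, a ratio of 0.67. Over 24 weeks it is (0.40 + 0.60)/(0.60 + 0.60) = 0.83.

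**The case against.** The strongest reply is that this is an ordinary consequence of an open-label add-on design and that the protocol already limits it. ECP participants attend for treatment and must be monitored then. SOC visits cover the whole period, and section 9.2 requires all adverse events from consent onwards to be recorded in both arms. Section 5.4.3 has sites collect medication changes, treatment changes, unscheduled assessments and admissions at every common visit, and section 5.1.1 describes direct short-notice access to the centre. Infections, transfusions and worsening of existing conditions often leave such a record and depend less on memory. The bias overstates ECP harm and does not conceal it. The telephone wording in 5.7 is permissive.

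Much of this stands, and it limits the size. A reader might infer that ECP rates are certain to be higher, or that ascertainment and treatment effect cannot be told apart at all. The documents support neither: they give no recall rate, and contacts are identical after week 12. That later period is only a partial substitute, however, because ECP cycles are then 4 weeks apart and no longer 2.

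Three parts do not stand. A duty to record events does not equalise how often participants are asked. The permissive wording concerns the telephone as a means; the Schedule of Events marks AE reporting at those weeks regardless. Nor can this be left to the analysis plan, because no analysis recovers SOC events that were never elicited.

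**Conclusion.** The concern holds as a modest, avoidable asymmetry. The 10 against 6 count is exact and the direction follows from the schedule. The size rests on assumed recall: about 1.0 to 1.17 over the 24 weeks that section 2.2 specifies, and 1.0 to 1.33 within weeks 0 to 12. The higher figure should not be read as the distortion of the 24-week outcome.

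It would also go too far to infer that serious events or the efficacy result are compromised. SAEs are reported within 24 hours of staff becoming aware and are little exposed to recall, and the primary endpoint is built from FEV1 and FVC. The point concerns non-serious, short-lived events, and the remedy is a cheap improvement to data collection.

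**What to change.** - In sections 5.4.1 and 5.7, add the same scripted telephone AE and medication check at weeks 2, 6 and 10 for SOC participants. With 90 randomised 1:1, that is about 45 × 3 = 135 short calls by existing site staff. The cost is this small workload and the added participant contact; no ECP monitoring is removed.
- Report AE rates per unit of follow-up from randomisation in both arms, because the follow-up clock starts at different points.
- Show events occurring during ECP sessions separately as well as in the total.
- Do not limit the between-arm comparison to events captured at common visits. It looks free, but it would bias the comparison in favour of ECP.
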